13.6 Safety Analysis and Stopping Rules for Excessive Toxicity

Following the phase I study, the early stopping rule for safety/toxicity will be assessed for each patient after cycle 1. The expected rate of unacceptable toxicity should not be $\geq 33\%$. Note: The phase II portion of the study will use the DLT definition to define unacceptable toxicity (see section 13.2). This rule is in addition to the quarterly review of all toxicities submitted to the COH DSMC. Given the number of patients treated, if the unacceptable toxicity rate is $\geq 33\%$, patient accrual will be halted and a full review of the data by the Data Safety Monitoring Committee (DSMC) will be mandated.

In addition, cumulative safety data will be reviewed on a quarterly basis in order to identify safety concerns that may emerge due to cumulative exposure.

13.7 Trial Statistical Analysis Plan

Patient demographic and baseline characteristics, including age, gender, medical history, and prior therapy, will be summarized using descriptive statistics. For continuous variables, descriptive statistics (number [n], mean, standard deviation, standard error, median (range) will be provided. For categorical variables, patient counts and percentages will be provided.

Phase I Analysis: Observed toxicities will be summarized in terms of type (organ affected or laboratory determination), severity, time of onset, duration, probable association with the study treatment and reversibility or outcome. Baseline information (e.g. the extent/type of prior therapy) and demographic information will be presented as well to describe the patients treated in this study.

Phase II Analysis: The complete remission (CR+CRi) rate will be calculated as the percent of evaluable patients; exact 95% confidence intervals will be calculated for these estimates. Response rates will also be evaluated based on number and type of prior therapy(ies). Time to response, duration of response, and survival will be estimated using the product-limit method of Kaplan and Meier.

Clinical Pharmacology Analysis Plan:

- Plasma, urine and cellular PK of 8-chloro-adenosine and metabolites will be quantitated as continual measurement variables as per assays described in Section 9.1.7.
- Descriptive statistics and graphical displays will be used to summarize levels of serum/urine 8-chloro-adenosine and its metabolites at each time point and to evaluate changes pre- post-treatment measurement. A paired t-test will be used to determine if there is a statistically significant change.
- Similar methods will be used to assess the PD impact of 8-chloro-adenosine on the cellular ATP pool and select short-lived mRNAs including corresponding proteins in AML blasts. Protein and mRNA levels will be summarized descriptively using means, medians, standard deviations and ranges.
- Summary statistics of the PK/PD parameters for the population will be derived from the parameters obtained from the individual patients.
- Results will also be summarized in terms of response and toxicity.
- To determine if there are dose-dependent changes in 8-chloro-ATP and 8-chloro-adenosine (when administered ex vivo), summary statistics and graphical displays will be generated to descriptively compare accumulation of 8-chloro-ATP and endogenous ATP levels in circulating AML blasts over 5 doses.
- Gene ontology (GO) and pathways will be analyzed using DAVID (Database for Annotation, Visualization, and Integrated Discovery), an online bioinformatic resource for functional interpretation of large lists of genes. Pathways and GO that correlate with response will be sorted by their multiple comparison adjusted p value. Potential miRNA targets will be identified using TargetScan and their functional annotation will be done using DAVID.
- All summaries will be exploratory in nature, with the goal of developing further questions regarding the modulation of therapy, or regarding reasons for efficacy or lack of efficacy.

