Clinical Pharmacology Analysis: Plasma, urinary and cellular PK of 8-chloro-adenosine and metabolites will be quantitated as continual measurement variables. Descriptive statistics and graphical displays will be used to summarize levels of serum/urine 8-chloro-adenosine and its metabolites at each time point and to evaluate changes over time. A paired t-test will be used to determine if there is a statistically significant change. Similar methods will be used to assess the PD impact of 8-chloro-adenosine on the cellular ATP pool and select short-lived mRNAs including corresponding proteins in AML blasts. Protein and mRNA levels will be summarized descriptively

using means, medians, standard deviations and ranges. Summary statistics of the PK/PD parameters for the population will be derived from the parameters obtained from the individual patients. Results will also be summarized in terms of response and toxicity. To determine if there are dose-dependent changes in 8-Cl-ATP and 8-chloro-adenosine (when administered ex vivo), summary statistics and graphical displays will be generated to descriptively compare accumulation of 8-Cl-ATP and endogenous ATP levels in circulating AML blasts over 5 doses.

Molecular Studies Analysis: Gene ontology (GO) and pathways will be analyzed using DAVID (Database for Annotation, Visualization, and Integrated Discovery), an online bioinformatic resource for functional interpretation of large lists of genes. Pathways and GO that correlate with response will be sorted by their multiple comparison adjusted p value. Potential miRNA targets will be identified using TargetScan and their functional annotation will be done using DAVID. All summaries will be exploratory in nature, with the goal of developing further questions regarding the modulation of therapy, or regarding reasons for efficacy or lack of efficacy.

Sponsor/Licensee:

Investigator Initiated: City of Hope

Case Report Forms

Medidata RAVE® Electronic Data Capture system.

TABLE OF CONTENTS

SECTION	PAGE
Experimental Design Schema	2
Protocol Synopsis.....	3
Table of Contents	11
Abbreviations.....	14
1.0 Goals and Objectives (Scientific Aims)	15
1.1 Primary Objectives	15
1.2 Secondary Objectives.....	15
1.3 Clinical Pharmacology Objectives (Phase I and II).....	15
1.4 Exploratory Ex-Vivo Molecular Objectives (Phase I and II)	15
2.0 Background.....	16
2.1 Acute Myeloid Leukemia.....	16
2.2 8-Chloro-adenosine.....	16
2.3 Overview and Rationale of Study Design	16

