2.4 Pharmacology of 8-Chloro-adenosine

2.4.1 Chemistry

Chemical Name: 8-chloro-adenosine

Other name: NSC 354258

Manufacturer: University of Iowa Pharmaceuticals

8-chloro-adenosine is an adenosine analogue with a ribose sugar and a chlorine group at the 8-position of the adenine base. 8-chloro-adenosine has a molecular formula $C_{10}H_{12}N_5O_4Cl$ and molecular weight of 301.68. The melting point is 198-199°C. It is a white powder that has an intrinsic solubility in water of 4.8 mg/ml. It is stable (no degradation) at 25°C or 35°C for at least 2 months, however, it is unstable in water at pH<3 and pH>8. A 5 mg/ml aqueous solution appears to be stable at pH 7.0 for over 1 year.

8-chloro-adenosine was prepared in a 3-step reaction from adenosine: 1) acetylation of adenosine with acetic anhydride; 2) reaction with m-chloro-phenylbenzoic acid/HCl to yield 8-chloro-adenosine triacetate; 3) deacetylation with sodium methoxide/methanol.

The drug is supplied at a concentration of 5 mg/mL in 5% dextrose (20 mL per vial).

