9.1.2 Blood Sample Collection

Blood samples will be collected from an indwelling venous catheter or by venipuncture, at a **separate anatomic** site as drug infusion e.g., in the opposite arm of the drug infusion. In cases of poor venous access, specimen may be drawn from a catheter lumen separate from that used for drug infusion after approval by PI. At each time point indicated in Table 9.1.2, peripheral blood will be collected into **three*** **7 ml green-top tubes** (sodium or lithium heparin) containing deoxycoformycin to prevent blood clotting and ex vivo deamination of 8-chloro-adenosine. Only one 7ml green top tube need be collected unless circulating blast count is over 5000/ μ L. Tubes will be **inverted several times** and then **immediately placed on ice** and brought **promptly** (so that the sample can be processed within the hour) to the CICSL (Shapiro rm. 1042) or other processing laboratory. Notify the CICSL ([name] or her representative) by e-mail to [contact] in advance of sampling (ideally >1 day in advance).

Table 9.1.2 Time Points of Blood Sample Collection for PK/PD Studies

Pt. MRN:	Pt. Initials (F, M, L):	Pt. Study ID:
----------	-------------------------	---------------

	Time Point During Cycle 1	No. of tubes collected*	Time (h:m of 24-hr clock)	Date	Initials
Day 1	0-24hr Pre-infusion				
	Start of Infusion TIME	--			
	Within last 15 minutes of infusion				
	End of Infusion (EOI) TIME#	--			
	1 hr post EOI +/- 15 min				
	3 hr post EOI +/- 15 min				
	6-8 hr post EOI				
Day 2	12-18 hr post EOI				
	0-1 hr pre-infusion				
	Start of Infusion TIME	--			
	Within last 15 minutes of infusion				
Day 3	End of Infusion TIME#	--			
	0-1 hr pre-infusion				
	Start of Infusion TIME	--			
	Within last 15 minutes of infusion				
Day 4	End of Infusion TIME#	--			
	0-1hr Pre-infusion				
	Start of Infusion TIME	--			
	Within last 15 minutes of infusion				
Day 5	End of Infusion TIME#	--			
	0-1hr Pre-infusion				
	Start of Infusion TIME	--			
	Within last 15 minutes of infusion				
	End of Infusion TIME#	--			

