9.1.3 Urine Specimen Collection

All urine will be collected in three 8 hr +/-30 min sequential intervals (e.g. 0-8 hrs, 8-16 hrs, and 16-24 hrs) during the first 24 hours after the first dose of cycle 1. Samples will be delivered to CICSL in Shapiro room 1042 at room temperature. Samples may be delivered to CICSL in a single batch.

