12.2 Response

The primary endpoint is complete remission rate (CR + CRi) and is based on the Döhner, 2010 criteria²⁴; calculated as the percent of evaluable patients that have confirmed CR or CRi.

Response criteria will be as follows:

CR: Bone marrow with < 5% blasts by morphology. ANC > 10³/µL, platelets ≥ 10⁵/µL

CRi: Bone marrow with < 5% blasts by morphology, not meeting blood count criteria for CR.

PR: Decrease of at 50% in bone marrow blasts

PD: Bone marrow blasts more than 20% and increase in blasts by over 50%.

HR: improvement in hematologic parameters, but not meeting criteria for PR.

Secondary activity endpoints for this study are as follows:

- Duration of response, defined as the time interval from the date of first documented response (CR+CRi) to documented disease relapse or death whichever occurs first.
- Overall survival, defined as the time interval from date of first dose of study drug to date of death from any cause.
- Event-free survival, defined as the time interval from date of first dose of study drug to first documented disease progression or death from any cause, whichever occurs first.
- Overall response rate (CR/CRI/PR), calculated as the percent of evaluable patients that have confirmed CR or CRi or PR.

12.3 Clinical Pharmacology Endpoints:

- For plasma PK, levels of 8-chloro-adenosine, its deaminated metabolite, 8-chloro-inosine, and its base 8-chloro-adenine will be quantitated in plasma during 5 days of therapy.
- For cellular PK, concentrations of 8-chloro-adenosine and 8-chloro-ATP will be quantitated in circulating leukemia cells in the peripheral blood.
- For urine PK, levels of 8-chloro-adenosine, its deaminated metabolite, 8-chloro-inosine, and its base 8-chloro-adenine will be quantitated in urine during the first 24 hours of therapy.
- For PD, the impact of therapy on endogenous ATP pools, as well as the effect on short-lived mRNA transcripts and proteins will be analyzed in circulating acute leukemia blasts.

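### The paired t-test on drug and metabolite levels has no defined pair; read as pre- versus post-treatment, it tests only whether drug is present in plasma and cannot be run for urine

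*Combined protocol and SAP*

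**What the plan says.** The clinical pharmacology part of Section 13.7 calls for descriptive statistics and graphs of the levels of "serum/urine 8-chloro-adenosine and its metabolites at each time point and to evaluate changes pre- post-treatment measurement. A paired t-test will be used" to decide whether a change is significant. The Protocol Synopsis, under Clinical Pharmacology Analysis, gives the same test a different purpose: "to evaluate changes over time. A paired t-test will be used to determine if there is a statistically significant change". Neither place says which two samples make up a pair.

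The analytes are set in Section 12.3: "levels of 8-chloro-adenosine, its deaminated metabolite, 8-chloro-inosine, and its base 8-chloro-adenine will be quantitated in plasma during 5 days of therapy". The same three are measured in urine.

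Table 9.1.2 lists 14 Cycle 1 blood samples. One precedes any drug, the Day 1 sample labelled "0-24hr Pre-infusion". The other 13 come after the first infusion has started. They include an end-of-infusion sample on each of Days 1 to 5 and a pre-infusion sample on each of Days 2 to 5.

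Section 9.1.3 collects urine in three 8-hour intervals "during the first 24 hours after the first dose of cycle 1". In Table 10.0, research urine is marked on Day 1 only, and footnote z repeats the post-dose timing.

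**The concern.** A paired t-test is informative when both members of the pair could plausibly take a range of values. Here the natural pre-treatment member is the level of a study drug before the first dose. Section 2.4.1 describes a manufactured compound ("8-chloro-adenosine was prepared in a 3-step reaction from adenosine"), and the documents describe no endogenous source of the drug or its chlorinated metabolites. A pre/post test on such levels has a null hypothesis that dosing itself makes false. A report could then state a significant change in drug level when levels were flat, rising or falling from day to day. For urine the stated test has no baseline member.

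The two wordings also leave the sponsor to choose the pair later, possibly after seeing the data. At stake is a p-value that is misleading (plasma) or cannot be computed (urine). The dose decision and the efficacy conclusion are not at stake.

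**Working it through.** The plan gives no alpha, sidedness, sample size or power for this test, so there is no stated figure to reproduce. The CVs, the two-sided 0.05 level and the half-lives below are assumptions, shown as ranges. The patient numbers are the plan's: 3 (a cohort), 6 (patients at the RP2D from phase I), 15 (expected phase I), 25 (phase II maximum), 43 (whole study).

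**1. Plasma, read as pre versus post.** With pre = 0 in every patient, each difference equals the post-dose level x. Then

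t = mean(x) / (SD(x)/√n) = √n / CV,

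which is the one-sample test of a mean of zero. A six-patient example run both ways gave identical results (t = 7.893, p = 0.000525). At n=6, CV 50%: √6/0.5 = 4.90, p = 0.0045. At n=25, CV 50%: √25/0.5 = 10.0, p = 4.9×10⁻¹⁰.

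Share of 20,000 simulated trials that reject (log-normal post-dose levels, pre = 0):

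| n | CV 30% | CV 50% | CV 100% |
|---|---|---|---|
| 3 | 86% | 54% | 22% |
| 6 | 100% | 99% | 79% |
| 15 | 100% | 100% | 99% |
| 25 | 100% | 100% | 99.9% |
| 43 | 100% | 100% | 100% |

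No day-to-day change enters these figures. A non-significant result in a small cohort would reflect small n and spread between patients, not absence of drug.

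**2. Urine, read as pre versus post.** Pre-dose collections: 0. Post-dose intervals: 3. Evaluable pre/post pairs: 0. This step needs no assumption.

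**3. Where a zero baseline does not apply.** A 4-hour infusion every 24 hours leaves 24 − 4 = 20 hours before the next one. The fraction of the end-of-infusion level then remaining is 2^(−20/t½), assuming simple exponential decline. The documents give no plasma half-life. The fraction is below 0.1% for a half-life of 1 to 2 h, 3% at 4 h, 31% at 12 h and 56% at 24 h. The Days 2 to 5 pre-infusion levels may therefore be measurable or not.

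**4. An informative contrast from the same samples.** Take the within-patient log ratio of Day 5 to Day 1 end-of-infusion level. Assume CV 50%, so the log variance is ln(1.25) = 0.223, with 51% of it within patients. The SD of the log ratio is √(2 × 0.51 × 0.223) = 0.477.

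- No true change: simulated rejection 4.9% at n=6 and 5.0% at n=25.
- True 1.5-fold accumulation (ln 1.5 = 0.405): 39% at n=6 and 98% at n=25. With CV from 30% to 100% and 40% of log variance within patients, power at n=25 runs from 100% down to 74%.
- Precision of the geometric mean ratio, as a multiply/divide factor exp(t₀.₉₇₅ × 0.477/√n): n=25, exp(2.064 × 0.477/5) = 1.22; n=6, exp(2.571 × 0.477/2.449) = 1.65; n=3, exp(4.303 × 0.477/1.732) = 3.3.

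An interval is useful near 25 patients and nearly empty in a cohort of 3.

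**The case against.** A reader might infer that every baseline in this analysis is zero by construction, that the test cannot show change over time, and that accumulation across the five infusions goes unanalysed. The documents do not support that reading.

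- The synopsis states change over time as the aim. Table 9.1.2 supplies pairs that would serve it, such as Day 1 and Day 5 end of infusion. Only the Day 1 pre-infusion sample is expected to be zero. Under the synopsis wording, successive urine intervals could also be paired.
- Section 13.7 plans descriptive statistics and displays at each time point, and a descriptive comparison of 8-chloro-ATP accumulation over the five doses. Section 9.1.7 plans non-compartmental and compartmental analysis of plasma, cellular and urinary data. What is missing is a named inferential contrast, not all analysis.
- Section 13.7 calls its summaries exploratory. The rules in Sections 13.3, 13.4 and 13.6 do not use this p-value. Section 2.3 says that the PK and PD studies may help in choosing the RP2D, but nothing links that choice to the t-test.
- Simulation is hardly needed to show that a positive quantity differs from zero, and its CVs are assumed.

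All of this stands and limits the point. It does not rescue the text: Section 13.7 states a pre/post test, names urine in it, and leaves the pair undefined.

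**Conclusion.** The point holds in a limited form and is of low severity. The pair is undefined, and the two descriptions disagree. On the wording of Section 13.7 the plasma test only asks whether drug is present, and it rejects in 79% to 100% of trials at n=6 and in at least 99.9% at n=25 for CVs of 30% to 100%, with nothing changing over the days. On the same wording the urine test has no pairs.

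The plasma part assumes that no patient had earlier exposure to this drug, which the eligibility criteria do not address explicitly. It also assumes that the pre-treatment value is the Day 1 sample. The urine part rests only on the pre/post wording and the collection schedule. The tests on the ATP pool, mRNA and proteins are outside the point, because those quantities have a real baseline before treatment.

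**What to change.** In Section 13.7 and the synopsis, remove the pre/post paired t-test for 8-chloro-adenosine and its metabolites, and give both places the same text.

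- **Plasma, main contrast:** within-patient log ratio of Day 5 to Day 1 end-of-infusion level, reported as a geometric mean ratio with 95% CI for patients at the RP2D, and descriptively in small dose cohorts.
- **Plasma, pre-infusion levels:** add the Day 5 to Day 2 ratio only for patients with both values above the quantification limit. State that limit; Section 2.6 gives only a detection limit of 1 ng/mL in neat standards. State the rule for values below it, for example no substitution, with the number of patients below the limit reported at each time point. Note that the ratio then describes only patients with measurable levels on both days.
- **Urine:** amount and percent of dose excreted in each interval and over 0 to 24 hours, descriptively, with no pre/post test. Section 9.1.4 already records the volume of each interval.

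Leave the ATP, mRNA and protein tests in place. The cost is wording in two places: no new samples or assays, and the loss of a p-value that carries almost no pharmacokinetic information.

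### The pre/post paired t-test of drug and metabolite levels cannot be run for urine and, in plasma, only asks whether drug was given

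*Combined protocol and SAP*

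**What the plan says.** The Clinical Pharmacology Analysis Plan in section 13.7 uses descriptive statistics and graphs to "summarize levels of serum/urine 8-chloro-adenosine and its metabolites at each time point and to evaluate changes pre- post-treatment measurement". The next sentence reads: "A paired t-test will be used to determine if there is a statistically significant change". It then extends similar methods to the cellular ATP pool, short-lived mRNAs and the corresponding proteins. The synopsis describes the same analysis differently: levels are summarised "at each time point and to evaluate changes over time", followed by the same t-test. Neither place names the pair of time points, the scale, the significance level, or what to do with values below quantification.

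The analytes are set out in section 12.3; for plasma, "levels of 8-chloro-adenosine, its deaminated metabolite, 8-chloro-inosine, and its base 8-chloro-adenine will be quantitated in plasma during 5 days of therapy". Urine, under section 9.1.3, is collected in three consecutive 8-hour intervals "during the first 24 hours after the first dose of cycle 1". In Table 9.1.2 the first Day 1 blood sample is "0-24hr Pre-infusion"; every other sample follows at least the start of the first infusion.

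**The concern.** A paired pre/post test needs two things: a pre-treatment value for each patient, and a null hypothesis of no change that could be true. The urine schedule does not supply the first. The plasma analytes do not allow the second, because nobody would expect to find the drug or its chlorinated metabolites before the first infusion.

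As written, then, the report would contain one test that cannot be produced and one whose answer says nothing about kinetics. The more useful question about drug levels is whether they build up over five daily infusions. Section 2.6 describes such build-up for cellular 8-Cl-ATP in the earlier CLL trial. The scheduled samples can address it, but the stated test does not.

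**Working it through.** The plan gives no sample size, power or significance level for this test, so there is no figure of its own to reproduce. The check sets the test against the sampling schedule and then works out what it would deliver.

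**Urine.** Intervals scheduled (section 9.1.3, and the urine footnote to Table 10.0): 0–8, 8–16 and 16–24 hours after the first dose of cycle 1. Pre-dose intervals: 0. Pre/post pairs per patient: 0. This needs no assumption.

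**Plasma.** Blood time points in Tables 9.1.2 and 9.1.4: 6 on Day 1 and 2 on each of Days 2–5, so 6 + 4 × 2 = 14.

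- Before any drug: 1 (Day 1). Table 9.1.4 labels only this sample as pretreatment.
- Pre-infusion but after earlier doses: 4 (Days 2–5).
- Under pre/post wording with no pair named, each of the 13 later samples could be set against Day 1 pre-dose for each of 3 analytes: 13 × 3 = 39 possible tests.

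**Expected Day 1 value.** Section 2.4.1 says that "8-chloro-adenosine was prepared in a 3-step reaction from adenosine", so the compound is synthetic and no endogenous level is expected. This is an inference; the documents report no pre-dose measurement.

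**What the test becomes.** If the pre-dose value is 0 for every patient, the paired difference is the post-dose level itself:

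- difference = post − 0 = post
- t = mean(post) / [SD(post) / √n], which is the one-sample test that the mean post-dose level is zero
- noncentrality = √n / CV, where CV is the between-patient coefficient of variation

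On simulated data the paired and one-sample tests gave identical p-values.

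**Power.** Assumptions not in the documents: two-sided 5% level and CV of 30% to 100%. Two worked cases from the noncentral t distribution:

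- n = 15, CV 100%: √15 / 1 = 3.87 on 14 degrees of freedom, power 94.9%
- n = 3, CV 30%: √3 / 0.3 = 5.77 on 2 degrees of freedom, power 81.3%

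| n | Noncentral t, CV 30% | Noncentral t, CV 100% | Log-normal simulation, CV 30% | Log-normal simulation, CV 100% |
|---|---|---|---|---|
| 3 | 81.3% | 17.9% | 86.3% | 21.9% |
| 15 | 100% | 94.9% | 100% | 99.4% |
| 25 | 100% | 99.8% | 100% | 99.9% |

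The simulation used 20,000 trials per cell. At the expected overall size of 43 it gave 100% for every CV tried. With patients pooled, rejection is close to certain whatever the kinetics. In a three-patient cohort, a non-significant result would reflect only the small n and the CV.

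**The case against.** Four objections carry weight.

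**The PK objective does not rest on this test.** A reader might infer that the PK objective is defeated. The documents do not support that. The objective in section 9.1.1 is to describe the pharmacokinetics. Section 9.1.7 does so with non-compartmental and compartmental parameters and a two-stage population summary. Section 13.7 also plans a descriptive look at 8-chloro-ATP accumulation and ATP levels over the five doses. The test is redundant for that objective, not harmful to it. This stands.

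**The pharmacodynamic measures are not affected.** A reader might extend the criticism to ATP, mRNA and protein. These are endogenous and have a real pretreatment sample, so a paired comparison is legitimate and addresses the ATP objective. The plan states no scale, so it cannot be faulted for choosing the raw one. This stands.

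**Other contrasts could be informative.** The synopsis wording is broad enough to allow trough-to-trough or peak-to-peak comparisons across days, and comparisons between urine intervals. The expected zero applies to only one blood sample in 14. This stands for the synopsis. Section 13.7, however, narrows the contrast to "to evaluate changes pre- post-treatment measurement", and the two texts disagree.

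**Significance is not guaranteed.** A reader might infer that the plasma test must always reject. In three-patient cohorts it need not, as the table shows. Near-certainty requires pooled patients or low variability.

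None of this gives the urine test a pre-treatment value, or makes the Day 1 plasma null a live hypothesis.

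**Conclusion.** The point holds in a narrow form. Under section 13.7, the pre/post t-test cannot be run for urine in any patient, and for plasma it tests a null that is false in advance. The urine part follows directly from the collection schedule. The plasma part rests on the inference that a synthetic compound is absent before the first dose, and the power figures rest on the assumed CV range and significance level.

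The size is minor. Section 13.7 calls its summaries exploratory. Section 2.3 says that the PK and PD studies may help in choosing the RP2D, but no rule for the MTD, the RP2D or the response endpoint uses this p-value. It remains worth correcting because the analysis is wrong as written, the synopsis and section 13.7 differ, and a better use of the same samples is available.

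**What to change.** Make the same edit in the synopsis (Clinical Pharmacology Analysis) and in section 13.7:

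1. Drop the pre/post t-test for 8-chloro-adenosine and its metabolites.
2. Summarise urine descriptively as amount excreted per interval (concentration × recorded volume). Section 9.1.4 already records the volume.
3. Estimate plasma and cellular accumulation as within-patient Day 5:Day 1 end-of-infusion geometric mean ratios with 95% confidence intervals. Add Day 5:Day 2 pre-infusion ratios where levels are quantifiable.
4. State a rule for values below the quantification limit. The trough ratio needs one: the documents give no plasma trough values, and they describe carry-over only for cellular 8-Cl-ATP.
5. Keep the paired comparison with the pretreatment sample for ATP, mRNA and protein. Reporting it as a log ratio with a 95% confidence interval is optional.

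The cost is a few sentences in two places and slightly more analysis work. No new samples are needed, because Table 9.1.2 already schedules these time points. One limit remains: cellular ratios will be available only in patients with at least 5000 circulating blasts per microliter, and only when cell processing is available.
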